9.4.4 SAFETY ANALYSES

Adverse Events

All safety analyses will be performed on the Safety set. No missing data handling approach will be applied.

The incidence of Adverse Events (AEs) and Serious Adverse Events (SAEs) recorded throughout the study will be presented overall and by treatment group. According to the onset date of the event, AEs will be defined as follows:

- Treatment-emergent AE: event with an onset date after treatment initiation
- Non-treatment-emergent AE: event with an onset date between informed consent and treatment initiation

Non-treatment-emergent AEs will be listed only.

Treatment-emergent AEs will be summarized by MedDRA dictionary system organ class and preferred term. A summary of treatment-emergent AEs by system organ class, preferred term and

severity will be also provided. All related treatment-emergent AEs, treatment-emergent SAEs, treatment-emergent AEs with an outcome of death, treatment-emergent AEs leading to treatment discontinuation will be summarized by MedDRA dictionary system organ class and preferred term and will also be listed.

All deaths will be listed together with all their details.

Intraocular pressure

The number of patients with a significant increase (> 6 mmHg) in intraocular pressure will be recorded and summarized descriptively. The comparison between test treatment and standard treatment in the incidence of significant increase of IOP will be made by means of 95% CI of the difference between treatments.

Visual acuity

The number of patients with a decrease in visual acuity measured as per local clinical practice will be recorded and summarized descriptively. The comparison between test treatment and standard treatment in the drop of visual acuity will be made by means of 95% CI of the difference between treatments.

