6.1.2 DOSING AND ADMINISTRATION

- ✤ Test arm
 - Levofloxacin + dexamethasone eye drops for 7 days, 1 drop 4 times a day (hours 8.00, 13.00, 18.00 and 23.00 ± 30 minutes), followed by dexamethasone eye drops alone (Maxidex[®]) for an additional 7 days, 1 drop 4 times a day (hours 8.00, 13.00, 18.00 and 23.00 ± 30 minutes).
- ✤ Control arm
 - Tobramycin + dexamethasone eye drops (Tobradex[®]) for 14 days, 1 drop 4 times a day (hours 8.00, 13.00, 18.00 and 23.00 ± 30 minutes).

In both arms, patients will start treatment according to local routine clinical practice, i.e. either immediately after randomization in those patients who are not bandaged after surgery, or soon after removal of dressing of operated eye. Doses administered on the same day as surgery will be considered additional to the full protocol dosage regimen (4 instillations per day for 14 days).

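### The treatment-emergent rule works by onset date and requires a date after treatment initiation, so adverse events starting on the first-drop day can drop out of the treatment-emergent tables

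*Combined protocol and SAP*

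**What the plan says.** Section 9.4.4 (Safety analyses, Adverse events) introduces the classification with "According to the onset date of the event, AEs will be defined as follows" and gives two classes:

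- "Treatment-emergent AE: event with an onset date after treatment initiation"
- "Non-treatment-emergent AE: event with an onset date between informed consent and treatment initiation"

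The two classes are reported differently. For the first, "Treatment-emergent AEs will be summarized by MedDRA dictionary system organ class and preferred term", with further summaries by severity and of related events, serious events, events with a fatal outcome and events leading to treatment discontinuation. For the second, "Non-treatment-emergent AEs will be listed only".

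The same section also promises a summary that is not limited to treatment-emergent events: "The incidence of Adverse Events (AEs) and Serious Adverse Events (SAEs) recorded throughout the study will be presented overall and by treatment group". On gaps in the safety data it says "No missing data handling approach will be applied".

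Section 6.1.2 sets the start of treatment by local practice: "either immediately after randomization in those patients who are not bandaged after surgery", or once the dressing has been removed. Drops given on the day of surgery come on top of the 14-day regimen, so that day can carry real exposure.

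**The concern.** The first-drop day is when an immediate reaction to the drops would begin, and the wording of the rule does not place that day in the treatment-emergent class.

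The protocol itself names reactions of this kind. Section 2.3.1 mentions burning on instillation for the comparator. Section 6.6 mentions eye irritation from benzalkonium chloride for all three products and, for systemic fluoroquinolones, hypersensitivity after a single dose. Section 7.1 lists hypersensitivity to the comparator and allergic reaction to the test combination as grounds for permanent discontinuation.

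If the rule is programmed as a comparison of calendar dates, an allergic reaction to the first drop that ends treatment would not appear in the table of treatment-emergent events leading to discontinuation. For a new fixed combination, that table should not depend on how a programmer reads one preposition.

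**Working it through.** The plan states no figure on this point, so there is none to reproduce. The check applies the rule to example onsets under each available reading.

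**Inputs.** Classification by onset date, the word *after*, and the undefined word *between* (section 9.4.4). First drop possibly on the day of surgery (section 6.1.2). Time of onset among the adverse event data collected (section 8.4.4). Instillation times recorded in the patient diary (section 4.1).

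**Step 1: classify three onsets.** Take a first drop at 14:00 (an invented time, for illustration only). TE means treatment-emergent.

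| Onset | Date only, strictly after | Date only, on or after | Date and time |
|---|---|---|---|
| Same day, 09:00 (before the drop) | not TE | TE | not TE |
| Same day, 15:00 (after the drop) | not TE | TE | TE |
| Next day, 09:00 | TE | TE | TE |

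The readings agree on the next-day event and disagree on the first-drop day. Under the strict date reading, a reaction one hour after the drop is treated like an event five hours before any exposure. Only that reading loses the 15:00 event.

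**Step 2: where the 15:00 event goes under the strict reading.** If *between* includes the day of initiation, the event is non-treatment-emergent and is listed only. If it excludes that day, the event belongs to neither class. Section 9.4.4 does not say which.

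**Step 3: which outputs change.**

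- Affected: the treatment-emergent summaries by system organ class and preferred term, by severity, of related events, of serious events, of events with a fatal outcome and of events leading to treatment discontinuation.
- Not affected: the overall by-arm incidence of adverse events and serious adverse events, which carries no treatment-emergent condition; the listing of all deaths; and the tolerability analysis (sections 8.3 and 9.4.5), which scores global tolerability and burning, stinging and blurred vision at Days 4, 8 and 15 and reports 95% confidence intervals.

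**Step 4: can the other readings be applied as the text stands?** The data for a date-and-time split appear to be collected. However, section 9.4.4 prescribes the onset date rather than the time, section 8.4.4 itself also speaks of onset dates, and no missing-data approach is allowed for safety. An event with no clock time therefore has no assigned class under the date-and-time reading.

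**The case against.** The strongest reply is that initiation is naturally an instant, the first drop, and that the sentence does not refer to the date of initiation. Onset times and instillation times are collected, so a careful programmer could split the first day correctly. This stands as far as it goes: on that reading nothing is lost, and the loss is therefore conditional. It does not settle the matter, because the section names the onset date as the basis and has no rule for a missing time.

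A reader might infer that every first-day event disappears from the by-arm safety results. The documents do not support that. The overall incidence of adverse events and serious adverse events is presented by group without restriction. Local burning, stinging and blurred vision are scored and analysed whatever their onset date. Itching/burning is also part of the ocular symptom score, and ocular pain is scored separately (section 8.2). These scores do not replace the adverse event tables for hypersensitivity or other serious reactions, and the first of them is taken only at Day 4.

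A reader might also want to put a percentage on the shortfall. No first-day event rate is given, so a share such as 10% to 30% of reactions would be pure assumption. Even then the shortfall would not simply equal that share. Drops are given four times a day, section 8.4.4 requires the onset of each episode of an intermittent event, and a later episode would bring the patient back into a patient-level count.

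Finally, section 9.3 defers the replacement of missing values to a statistical analysis plan, and derivation rules might be settled there too. That is possible but not shown, and the rule in section 9.4.4 is stated as it is.

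**Conclusion.** The point holds as a defect in a stated rule, with a conditional consequence. Read literally by date, section 9.4.4 removes events that start on the first-drop day from every treatment-emergent table and leaves it unclear whether they are listed or unclassified. Read by clock time, it does not. Two programmers could both follow the plan and produce different safety tables.

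The size cannot be computed, because the documents give neither the number nor the share of events with onset on that day. Allocation is 1:1, stratified by center, and the rule is the same in both arms, so the expected effect under the strict reading is understated absolute rates in both. A built-in bias toward one arm does not follow, although any real difference in first-day reactions would be absent from those tables.

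The conclusion assumes that section 9.4.4 is the operative definition and that no later document overrides it.

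**What to change.** In section 9.4.4, define a treatment-emergent adverse event as one whose onset date is on or after the date of the first study drop. Exclude an event dated that day only if its recorded onset time shows that it preceded the first drop. Count a same-day event with a missing onset time as treatment-emergent, and state this as an exception to the sentence that rules out missing-data handling for safety. Define the non-treatment-emergent class as every other event from consent onward, so that no event falls between the two.

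In the example above, the 15:00 and next-day events become treatment-emergent, the 09:00 event stays out if its time is recorded, and a same-day event without a time is counted.

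The change uses information that the plan already collects. The first-drop date and time from the diary must be available to the analysis. The cost falls mainly on patients whose first drop follows surgery on the same day: some events of that day, including surgical ones with no recorded time, will enter both arms' tables. Reported rates will rise slightly, and the contrast between arms may be slightly diluted.

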8.4.4 TIME PERIOD AND FREQUENCY FOR EVENT ASSESSMENT AND FOLLOW-UP

The occurrence of an adverse event (AE) or serious adverse event (SAE) may come to the attention of study personnel during study visits and interviews of a study participant presenting for medical care, or upon review by a study monitor.

All AEs including local and systemic reactions will be captured on the eCRF. Information to be collected includes event description, time of onset, clinician's assessment of severity, relationship to study product (assessed only by those with the training and authority to make a diagnosis), and time of resolution/stabilization of the event. All AEs occurring while on study must be documented appropriately regardless of relationship. All AEs will be followed to adequate resolution.

Any medical condition that is present at the time that the participant is screened will be considered as baseline and not reported as an AE. However, if the study participant's condition deteriorates at any time during the study, it will be recorded as an AE.

Changes in the severity of an AE will be documented to allow an assessment of the duration of the event at each level of severity. AEs characterized as intermittent require documentation of onset and duration of each episode.

The investigator will record all reportable events with onset dates occurring any time after informed consent is obtained until 7 (for non-serious AEs) or 30 days (for SAEs) after the last day of study participation. At each study visit, the investigator will inquire about the occurrence of AE/SAEs since the previous visit. Events will be followed for outcome information until resolution or stabilization.

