9.4 STATISTICAL ANALYSES

9.4.1 GENERAL APPROACH

Continuous data will be summarized with standard descriptive statistics (i.e. the mean, standard deviation, minimum, median and maximum, 95% confidence limits). Categorical data will be summarized by frequencies and percentages.

No statistical test will be performed for between-group differences in demographic and baseline features (medical history and efficacy data).

Medical history and adverse events will be described according to System Organ Classes (SOC) and Preferred Terms (PT) using the Medical Dictionary for Regulatory Activities (MedDRA) and will be presented by treatment group.

Previous/concomitant medications will be presented by treatment group using the World Health Organization Drug Dictionary (WHO-DD).

All analysis will be performed using SAS version 9.4 or later.

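### Treatment-emergent AEs are defined by onset date only, so a continuous AE that begins before the first drop and worsens on study drug is left out of the six detailed by-arm AE tables

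*Combined protocol and SAP*

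**What the plan says.** Section 9.4.4 (Safety Analyses) makes onset date the only criterion: "Treatment-emergent AE: event with an onset date after treatment initiation". An AE whose onset lies between consent and the start of treatment falls into the complementary class, and "Non-treatment-emergent AEs will be listed only". The detailed summaries that follow are all built on the treatment-emergent class. They cover SOC/PT, SOC/PT by severity, and related events, and in addition "treatment-emergent SAEs, treatment-emergent AEs with an outcome of death, treatment-emergent AEs leading to treatment discontinuation will be summarized".

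Two general sentences carry no such restriction. Section 9.4.4 opens with "The incidence of Adverse Events (AEs) and Serious Adverse Events (SAEs) recorded throughout the study will be presented overall and by treatment group". Section 9.4.1 says "Medical history and adverse events will be described according to System Organ Classes (SOC) and Preferred Terms (PT"), presented by treatment group.

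The recording rules are in section 8.4.4. A condition present at screening is baseline and not an AE, but "However, if the study participant's condition deteriorates at any time during the study, it will be recorded as an AE". For an AE already on record, "Changes in the severity of an AE will be documented to allow an assessment of the duration of the event at each level of severity". For recurrent events, "AEs characterized as intermittent require documentation of onset and duration of each episode".

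**The concern.** A treatment-emergent definition should pick up what changes for the worse once study drug is on board. A definition based on onset alone does that only for events that begin on drug. An event that was mild before the first drop and became severe, serious or a reason for stopping during treatment is also on-treatment information, and the tables by severity, seriousness and discontinuation exist to show it by arm.

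The window in which such events can begin is not empty. AEs are collected from consent, and screening may take place up to 28 days before surgery (section 1.3). Surgery itself precedes the first drop, and bandaged patients start only when the dressing comes off (section 6.1.2).

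Evaluating the safety of the new combination is a stated objective (section 3). A reader comparing the arms from the detailed tables would not see these events and would have to find them in the listings.

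**Working it through.** No arithmetic applies. The check is to apply the recording rule in 8.4.4 and then the classification rule in 9.4.4 to each type of event in a patient in the Safety set.

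1. **Event begins after the first drop.** Its onset is after treatment initiation, so it is treatment-emergent and is tabulated. There is no problem.

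2. **Condition present at screening deteriorates on drug.** Section 8.4.4 makes the deterioration an AE. The deterioration occurs on drug, so the AE can carry an on-drug onset and count as treatment-emergent.

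3. **Intermittent AE, first episode before the first drop, later episode on drug.** Section 8.4.4 requires an onset for each episode, so the later episode has an on-drug onset and can be counted.

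4. **Continuous AE that begins after screening but before the first drop and worsens on drug.** It was not present at screening, so the baseline rule does not apply. It is already an AE, and 8.4.4 asks for its severity changes to be documented so that time at each severity level can be assessed. That describes one event with several levels, not a second event with a new onset. Section 8.4.6 points the same way for events that are already serious: progression is reported as follow-up to the original episode. The onset stays before treatment, so under 9.4.4 the event is non-treatment-emergent and goes to a listing.

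Cases 2 and 4 differ only in whether the problem existed at screening or arose shortly afterwards. The on-drug course may be identical, yet only case 2 can reach the tables.

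**Reach of the rule in case 4.** The detailed summaries in 9.4.4 are:

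- (1) SOC/PT
- (2) SOC/PT by severity
- (3) related
- (4) SAEs
- (5) outcome of death
- (6) leading to treatment discontinuation

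All six are restricted to treatment-emergent AEs, so a case 4 event is absent from all six. The opening by-arm incidence statement in 9.4.4 is a separate presentation with no such restriction and is not part of this count.

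**How many events are affected.** The documents give no rate for AEs that begin before the first drop and worsen on treatment, so no number of patients is derived.

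**The case against.** The case for leaving the text alone has five parts.

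- **The event may still be counted by arm.** The opening sentence of 9.4.4 and the general statement in 9.4.1 present AEs by treatment group without limiting them to treatment-emergent events. A reader might infer from the classification rule that these events disappear from every by-arm AE summary. The documents do not support that, because an overall incidence could include them. The listing rule is more specific and points the other way, so the position is ambiguous. The six detailed tables omit the event on either reading.

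- **A site may open a new AE.** The deterioration sentence in 8.4.4 is broadly worded, and 7.1 has new clinically relevant findings reported as AEs. Some worsened events may gain an on-drug onset in this way. But the deterioration sentence follows directly from the rule on conditions present at screening, and simple worsening of a known AE is not obviously a new finding. Leaving this to site practice also makes classification inconsistent between sites.

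- **Few events qualify.** Eligibility is rechecked on the day of surgery (8.1), exclusion 1 removes interfering ocular conditions at the investigator's discretion (5.2), and only uncomplicated surgeries are randomized (5.1.2). This stands. What remains is mainly systemic events, minor ocular events, and events between surgery and the first drop. For systemic events, section 2.2 describes plasma levels as negligible, so a hidden drug signal is unlikely.

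- **Other analyses cover much of the ground.** Endophthalmitis, hyperemia, symptoms, pain, rescue use, IOP, visual acuity and tolerability are analysed separately, whatever the AE onset date, and all deaths are listed. This also stands, but these outcomes do not stand in for AEs in general.

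- **A separate analysis plan may define the flag more fully.** Section 9.3 mentions such a plan, but only for replacing missing values. The AE definition is given in 9.4.4 without deferral. A fuller definition elsewhere cannot be excluded.

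**Conclusion.** The gap is real and narrow. As written, a continuous AE that begins after screening but before the first drop, and then worsens, becomes serious or leads to stopping on study drug, is left out of the six detailed treatment-emergent tables. Its place in the general by-arm incidence is unclear.

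This rests on two assumptions: that sites follow the natural reading of 8.4.4 and keep one record with one onset for a continuous event, and that no later document replaces the 9.4.4 definition.

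The effect is probably small and cannot be quantified from the documents. It is confined to descriptive AE tables. A reader might infer that the safety comparison as a whole is compromised or that serious events go unreported. Neither follows. The events are still listed, SAE and SUSAR reporting under 8.4.6 does not use this flag, and the primary non-inferiority conclusion does not depend on it. The change is still worth making, because it is cheap and settles before database lock which events count.

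**What to change.** In 9.4.4, define a treatment-emergent AE as one that starts after the first dose of study drug, or one that starts earlier and, after the first dose, does any of the following: increases in severity, becomes serious, is newly judged related to study drug, or leads to treatment discontinuation or death. Tabulate it at its worst on-treatment severity. The last three triggers matter because a clause limited to severity and seriousness would miss an event that leads to stopping, or is judged related, without changing grade. State also whether the opening by-arm incidence in 9.4.4 covers all AEs from consent or only treatment-emergent ones.

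The cost is a sentence or two of text and a small change to the flag derivation. Severity changes are already documented under 8.4.4, relationship is assessed for every AE under 8.4.3.2, and SAEs are reported under 8.4.6, so no new visits or assessments are needed. The eCRF layout is not in the documents, so the programmer should confirm that the dates of these changes can be retrieved. The downside is that treatment-emergent counts rise slightly in both arms and will include some natural post-operative worsening.
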